10.2. Protocol Deviations

Protocol deviations will be tracked by the study team throughout the conduct of the study in accordance with the Protocol Deviation Management Plan [Version 8; 19JUL2018].

- Data will be reviewed prior to unblinding and freezing the database to ensure all important deviations are captured and categorized on the protocol deviations dataset.
- This INFORM dataset (DV) will be the basis for the summaries and listings of protocol deviations.

The percent of subjects who experience an important protocol deviation will be presented by treatment arm for the treatment period. The table will display the number and percentage of subjects with any important protocol deviation and each deviation type. A listing of subjects with an important protocol deviation will be provided by treatment group.

10.3. Demographic and Baseline Characteristics

Descriptive statistics will be used to summarize the continuous demographic and baseline characteristics of age (years) and weight (kg). Counts and percentages of the following categorical demographic and baseline characteristics will be presented: country region/country, gender, Hispanic or Latino origin, age group (≤ 45 years, $>45 - <65$ years and ≥ 65 years and then within this last group: $\geq 65 - <75$ years and ≥ 75 years) and race (Black or Other; see Section 8.3).

The above summary of demographic and baseline characteristics will be repeated for the following subgroups, where the subgroup categories are defined in Section 8.3:

- Age
- Gender

- Race
- Region
- SELENA SLEDAI
- Baseline steroid dose (based on systemic steroids used to treat SLE)

The number and percentage of subjects reporting each race and racial combination will be summarized. For subjects who check more than one race category, the race hierarchy rule defined in Section 9.5.10 will apply for this summary. Note that this differs to the handling of the race subgroup which ignores the hierarchy rule.

A standard summary of the number and percentage of subjects by age ranges Adolescents (12-17 Years), Adult (18– 64 Years), from 65 – 84 Years and ≥ 85 Years will be provided for disclosure purposes.

A summary of the number and percentage of subjects reporting current medical conditions and a separate summary of number and percentage of subjects reporting past medical conditions will be provided. A summary of the history of tobacco usage will also be provided.

A summary of the randomization stratification factors [screening SELENA SLEDAI score (≤ 9 vs. ≥ 10), region (US/Canada vs Central America/South America/Mexico vs Europe/Australia/Israel vs Asia), and steroid dose (≤ 7.5 mg/day vs > 7.5 mg/day prednisone or equivalent)] will be presented per the randomization and eCRF data.

A cross-tabulation of stratification factors will also be produced summarizing the categories of the randomization strata from IXRS to the eCRF strata for SELENA SLEDAI score (≤ 9 vs. ≥ 10), region (US/Canada vs Central America/South America/Mexico vs Europe/Australia/Israel vs Asia), and steroid dose (≤ 7.5 mg/day vs > 7.5 mg/day prednisone or equivalent).

Note that for stratification factors summaries, the steroid dose will be derived from the eCRF considering steroids received for SLE only, whereas the randomization strata were derived by sites considering all steroids.

Demographic and baseline characteristics (age, gender, ethnicity, weight, race [black vs. other]), as well as stratification factors per IXRS, will be listed by subject. Race as assigned using the hierarchy rule (Section 9.5.10) will be listed by subject. Current and past medical conditions and tobacco use history will be listed by subject.

A summary of baseline disease activity will be provided, including counts and percentages for screening SELENA SLEDAI category (≤ 9 , ≥ 10), complement levels (Low, Not Low), anti-dsDNA (High, Not High), complement and anti-dsDNA (Low Complement and High Anti-dsDNA, Not (Low Complement and High Anti-dsDNA)). and univariate statistics for SLE disease duration (years), screening SELENA SLEDAI total score, and SLICC/ACR Damage Index. This summary will be repeated for the following subgroups, where the subgroup categories are defined in Section 8.3:

- Age
- Gender
- Race
- Region
- SELENA SLEDAI
- Baseline steroid dose (based on systemic steroids used to treat SLE)

The following indicators of baseline disease activity will also be summarized:

- Screening SELENA SLEDAI category by organ domain and item (count and percentage with each item present)
- Baseline SLICC by organ domain and item (count and percentage with each item present)
- Allowable SLE medication usage (see [Appendix 3: SLE Allowable Medication Categories](#)) at baseline – counts and percentages by class (Steroids, Anti-Malarials, and Other Immunosuppressive/Immunomodulatory Agents, Aspirin and NSAIDs) and drug as well as summary statistics for average daily prednisone dose (mg/day) (see [Section 9.5.16.1](#) for derivation of average daily prednisone equivalent dose) at baseline and counts and percentages for average daily prednisone dose (mg/day) at baseline (0, >0 - ≤7.5, >7.5). See [Appendix 4: Prednisone Equivalent Conversion](#) for instructions on converting steroids to prednisone equivalents. Only steroids with medication type corticosteroid for SLE will be included. Only immunomodulatory modulatory medications used to treat SLE will be included. For other medications, all medication types will be included.
- Steroid, Anti-malarial and Immunosuppressant use at Baseline – counts and percentages by class (No Steroid, Immunosuppressant or Anti-malarial use, Steroid Only, Immunosuppressant Only, Anti-malarial Only, Steroid and Immunosuppressant Only, Steroid and Anti-Malarial Only, Immunosuppressant and Anti-Malarial Only, Steroid and Immunosuppressant and Anti-malarial). Only steroids with medication type corticosteroid for SLE will be included. Only immunomodulatory modulatory medications used to treat SLE will be included. For other medications, all medication types will be included.

Screening Columbia Suicide Severity Rating Scale (C-SSRS) scores by behavior and ideation components for lifetime and current (counts and percentages) will be presented.

Day 1 C-SSRS components since last visit will be summarized using counts and percentages.

In the screening (lifetime/current) and Day 1 C-SSRS summaries, the number (%) of subjects reporting each individual suicidal ideation (1-5) or behavior (6-10) will be presented (as opposed to the maximum ideation/behavior score).

A listing of screening SELENA SLEDAI results will be provided, including result for individual items and total score.

10.4. Concomitant Medications

Concomitant medications will be coded per drug name as defined in the GSK Drug Dictionary, and classified per the GSK-Drug ATC classification level 1 and ATC level 4. Concomitant medications are defined as medications that start on or before the first dose date of study treatment, and end on or after the first dose date of study treatment, or medications that start after the first dose date of study treatment. Note that medications with partial or missing start and/or stop dates will be assumed to be concomitant unless there is evidence through comparison of partial dates to suggest otherwise, for example, if the day is missing, then the month and year will be compared to the month and year of the first dose date of study treatment and if the month and year are the same or later, then the medication will be considered concomitant. See Section 9.4.3 for handling of missing and partial dates. Medications in the database that are determined to not be concomitant will be excluded from table summaries but included in the listing.

A summary of the number and percentage of subjects with concomitant medications by ATC level 1 term and ATC level 4 term will be displayed for the On-Study period. A further summary of concomitant medications by ATC level 4 term and preferred term will be provided for the on-study period (to Week 52). A listing of all concomitant medication data will be displayed by treatment and subject.

Commercial Benlysta is prohibited during the 52-week treatment period of the study, however, if subjects withdraw from IP and begin receiving it they can continue monthly visits as per the study calendar. As such, a listing of subjects who receive commercial Benlysta during the 52-week treatment period will be reported (from both the concomitant medication and the Years 2 to 5 CRF follow-up forms) with the caveat that the Years 2 to 5 data will not be locked at the time of reporting.

10.5. Extent of Exposure

The extent of exposure to study treatment through Week 52 will be assessed by examining the duration of exposure to belimumab/placebo in days and the total number of infusions a subject receives. Note that receipt of commercial Benlysta will not be included in exposure calculations.

Duration of exposure in days will be calculated as:

$$\text{Duration of exposure (days)} = \text{Last infusion date} - \text{First infusion date} + 28.$$

Only complete dates will be used when calculating duration of exposure. First and last infusion dates will be used, regardless of any missed doses.

If a subject has more than one infusion on any given day (i.e. infusion is stopped and then restarted), this will be counted as a single infusion in summaries but both infusions will be listed.

Where a partial infusion is received, this will be counted as one infusion in the calculation of number of infusions.

The duration of exposure and the total number of infusions will be summarized using descriptive statistics for the ITT population. The total number of infusions will also be summarized using counts and percentages using the following categories: 1 – 5 doses, 6 – 10 doses and, 11-14 doses.

Subject level exposure data will be listed for all subjects by treatment group and subjects using the Randomized population, flagging subjects whose treatment group differs from the As-Treated population. A listing of study agent administration, including whether total dose was administered and if not the reason why, will be provided. A listing of subjects for whom the blind was broken will also be provided.

11. PRIMARY AND OTHER SAFETY ANALYSES

AESI are defined endpoints in the protocol (and clarified in Section 2.2.3). There are also AESI defined in the Benlysta PSAP (Section 15 and Section 16; see Appendix 6: PSAP Sections for AESI Reporting), which overlap with the protocol-defined AESIs.

Analyses and summaries described in Section 11.1.2 will use the protocol-defined AESIs. All safety data from the AE dataset will be displayed in summaries described in Section 11.2.1. This is expected to cover protocol-defined AESIs and SAEs and additionally, though not anticipated, any non-serious AEs which were not in scope for collection in the protocol but remained on the database at database release. The required PSAP summaries for AESI are described in Section 11.2.4.

The primary study summaries will be of overall subject incidence rates of all-cause mortality and AESIs during the on-treatment period, with supportive summaries during the on-study period. SAEs will be descriptively summarized during the on-treatment and on-study periods.

Safety will also be reported using more detailed summaries of deaths, AESIs (per PSAP), and standard summaries of SAEs. Since there is targeted collection of AEs in the study i.e. AESIs and SAEs, this will be clarified where applicable.

To allow comparison with other studies in the Benlysta program, the format and content of the more detailed AESI summaries will be per PSAP standards. Therefore, data on the primary safety endpoints may be contained both at a high level within Section 11.1 and in more detail in Section 11.2.

Safety analysis will be performed on the As-Treated population.

The extent of missing follow-up data (i.e. for subjects who have withdrawn from the study prior to the Week 52 visit) and off-treatment data will be summarized by treatment group. Exploratory analyses may be performed to characterize the potential impact of off-treatment and missing data on the primary mortality endpoint results (see Appendix 7, Mortality Missing Data Exploratory Sensitivity Analyses).

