5.6. Other Considerations for Data Analyses and Data Handling Conventions

- All data summaries and analyses will be performed using the latest available version of SAS software (as available at GSK).
- Data displays will follow the shells outlined in the Mock TLFs document which will follow the Benlysta program standards and, as far as possible, follow the agreements proposed by the GSK Integrated Data Standards Library (IDSL).
- The most current version of Medical Dictionary for Regulatory Activities (MedDRA) at the time of DBF will be used for reporting.
- The most current version of the Benlysta PSAP at the time of DBF will be used for reporting.
- Where SDTM terminology differs from the eCRF and/or mock shells, the SDTM terminology will be presented in displays unless otherwise specified.

Unless otherwise stated, the following will apply:

- Continuous variables will be summarized with the statistics mean, median, standard deviation (SD), 25th and 75th percentiles, minimum and maximum.
- Categorical variables will be summarized with frequency counts and percentages, or proportions where specified. A 'Missing' category will be added to frequency counts if there is at least one missing record.
- Percentages will be calculated using the number of subjects in the relevant population/treatment group (denoted by N) as the denominator, unless otherwise stated.
- The minimum and maximum will be reported to the same number of decimal places as the raw data recorded in the database.
- The mean, median, 25th percentile and 75th percentile will be reported to one more decimal place than the raw data recorded in the database.
- The SD will be reported to two more decimal places than the raw data recorded in the database.
- A maximum of four decimal places will be used.
- Percentages will be presented to one decimal place unless otherwise specified (i.e. deaths and malignancies will be presented to 2 decimal places). Incidence rates will be presented to two decimal places.
- A count of zero will have no corresponding percentage.
- Listings will be based on the As-Treated population (unless otherwise specified) and generally be limited to those required by ICH guidelines and will be sorted by treatment group, investigator number, subject number and visit (where appropriate).

MedDRA Coding of Death and Malignancy:

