8. GENERAL CONSIDERATIONS FOR DATA ANALYSES

- All data summaries and analyses will be performed using the latest available version of SAS software (as available at GSK).
- Data displays will follow the shells outlined in the Mock TLFs document which will follow the Benlysta program standards and, as far as possible, follow the agreements proposed by the GSK Integrated Data Standards Library (IDSL).
- The most current version of MedDRA at the time of DBF will be used for reporting.
- The most current version of the Benlysta PSAP at the time of DBF will be used for reporting.
- Where SDTM terminology differs from the eCRF and/or mock shells, the SDTM terminology will be presented in displays unless otherwise specified.

Unless otherwise stated, the following will apply:

- Continuous variables will be summarized with the statistics mean, median, standard deviation (SD), 25th and 75th percentiles, minimum and maximum.
- Categorical variables will be summarized with frequency counts and percentages, or proportions where specified. A 'Missing' category will be added to frequency counts if there is at least one missing record.
- Percentages will be calculated using the number of subjects in the relevant population/treatment group (denoted by N) as the denominator, unless otherwise stated.
- The minimum and maximum will be reported to the same number of decimal places as the raw data recorded in the database.
- The mean, median, 25th percentile and 75th percentile will be reported to one more decimal place than the raw data recorded in the database.
- The SD will be reported to two more decimal places than the raw data recorded in the database.
- A maximum of four decimal places will be used.
- The same rules apply to scores calculated in the derived datasets.
- Percentages will be presented to one decimal place. Incidence rates and difference in incidence rates for the primary analyses will be presented to two decimal places.
- A count of zero will have no corresponding percentage.
- For statistical analyses, all tests will be two-sided and p-values will be presented to a maximum of 4 decimal places.
- Listings will be based on the Randomized population and generally be limited to those required by ICH guidelines and will be sorted by treatment group, investigator number, subject number and visit (where appropriate).

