On-Treatment	
All data:
 
 • Study Treatment Start Date ≤ Date ≤ minimum (Date of Death, Study Treatment Stop Date + 28 days)

Note: After study withdrawal or last exposure plus 28 days (whichever occurs later) if AESIs and SAEs are recorded, other than mortality and malignancy, these will not be included in the on-study period. See Section 11.2.1 for further detail on how these events will be handled.

Note: For mortality, date of death will be derived as the end date of the SAE with fatal outcome.

Note: Each study treatment infusion should have a start date and end date recorded, but in some cases only one variable is completed. The study treatment stop date is the date of the final study treatment infusion (taken as the first non-missing date of the final study treatment infusion start or end date).

Note: Only dates will be used to identify start and end of treatment (times will not be considered).

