9.5.14. Incidence Rate

Event incidence rates and subject incidence rates will be calculated for Mortality and Malignancy and other AESIs during the on-treatment and on-study (to Week 52) periods as defined below. Note, for Mortality only subject incidence rates will be calculated. Subject incidence rates will also be calculated for SAEs during the on-treatment and on-study periods at the SOC level only.

Typically for subject incidence rates the subject years would be censored at the time of the event for subjects who experience the event i.e. the subject years contributed to the incidence rate calculation for a subject would be the total years from treatment start date to the event date. However, in consideration of the low number of events, this additional adjustment is not anticipated to have a significant impact. Therefore, the additional adjustment will not be used and the subject years contributed by a subject with an event will be the total years from treatment start date to the end of the treatment period of interest for all AESIs and mortality.

On-treatment

$$\text{Subject Incidence Rate} = 100 \times \frac{\text{Number of Subjects with an Event}}{\text{Overall Subject Years On – Treatment}}$$

$$\text{Event Incidence Rate} = 100 \times \frac{\text{Number of Events}}{\text{Overall Subject Years On – Treatment}}$$

Where overall subject years of on-treatment follow-up =

$$\sum_{\text{all subjects in population}} [\text{on-treatment follow-up in years}]$$

See Section 9.5.4 for detail on the calculation of on-treatment follow-up.

On-study (to Week 52)

$$\text{Subject Incidence Rate} = 100 \times \frac{\text{Number of Subjects with an Event}}{\text{Overall Subject Years On – Study}}$$

$$\text{Event Incidence Rate} = 100 \times \frac{\text{Number of Events}}{\text{Overall Subject Years On – Study}}$$

Where overall subject years on-study =

$$\sum_{\text{all subjects in population}} [\text{on-study follow-up in years}]$$

See Section 9.5.4 for detail on the calculation of on-study follow-up.

As described in Section 9.1.1, the on-study follow-up (to Week 52) will be different for Mortality and Malignancy compared with other AESIs. This is expected because subjects who withdraw from the study may re-consent to be followed up at Week 52 where only mortality and malignancy data are collected.

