11.1. Primary Analysis: All-Cause Mortality, AESI and SAEs

The primary analyses will be performed for both the on-treatment and on-study periods, as defined in Section 9.1. The primary interest is in the on-treatment period, with the on-study considered an important supportive analysis.

The primary analyses for the on-treatment period will be repeated for subgroups as defined in Section 8.3. Follow-up adjusted summaries (i.e. subject incidence rate/event incidence rate) will not be included in subgroup tables.

An overall Double Dotplot for the percentage of subjects with an event will be provided for mortality and other AESIs for the on-treatment period. This is a panel display with two associated dot-plots; the left-hand panel will show the percentage of subjects with an event in each arm. The right-hand panel will show the difference in percentages, with bars for the 95% confidence interval around the difference. All AESIs and mortality will be displayed on the same plot. Further detail on methodology is given in Section 11.1.1 and Section 11.1.2.

An overall Double Dotplot for exposure-adjusted subject incidence rate will be provided for mortality and other AESIs for the on-treatment period. This is a panel display with two associated dot-plots; the left-hand panel will show the exposure-adjusted subject incidence rate in each arm. The right-hand panel will show the difference in the exposure-adjusted subject incidence rate, with bars for the 95% confidence interval around the difference. All AESIs and mortality will be displayed on the same plot. Further detail on methodology is given in Section 11.1.1 and Section 11.1.2.

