11.1.1. All-Cause Mortality

See Section 11.2.1 and Section 11.2.2 for further summaries and listings of deaths.

Percentages

A summary of the number and percentage of subjects who have died will be provided for belimumab and placebo as well as the difference in the percentage of subjects between the belimumab and placebo groups. The difference in percentages will be evaluated with a 2-sided 95% CI, using the simple asymptotic Chi-Square (Pearson) method [Newcombe, 1998]. This will be considered as the primary method of assessment of the treatment difference.

Subject Incidence Rate

Whilst a difference between belimumab and placebo groups in IP exposure and overall study duration (to Week 52) is not anticipated, to account for this, supplemental summaries using subject incidence rates will be provided.

The subject incidence rate of mortality per 100 subject years will be provided for belimumab and placebo as well as the difference between belimumab and placebo with 95% CIs. For within-group rates per 100 subject years, the 95% CI will be obtained via

on an exact Poisson method [Stokes, 2012]. For differences in rates between groups, the 95% CI will be constructed using a Normal approximation (Wald's method, [Liu, 2006]).

See Section 9.5.14 for further details on the calculation of incidence rates for the on-treatment and on-study periods.

Kaplan-Meier Figure

A plot of the Kaplan-Meier curve, including standard error bands, for all-cause mortality for belimumab and placebo will be provided to show the change in risk over time. The Kaplan-Meier estimates table will be outputted for quality control purposes but will not be used included in the tables or listings.

Time to Event is defined for the On-Treatment Period and On-Study Period as follows:

- For subjects who died during the evaluation period of interest (i.e. on-treatment or on-study): Time to event is the date of death - first exposure date + 1.
- For subjects who did not die or died after the end of the evaluation period of interest (i.e. on-treatment or on-study): Time to event (censored) is the censoring date – first exposure date + 1.

Occurrence and date of death will be determined based on the AE dataset where outcome = fatal (date of death will be derived as the end date of the SAE with fatal outcome).

The censoring date will be assigned based on the evaluation period of interest as follows:

- **On-treatment:** end date for On-Treatment period (see Section 9.1.1)

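### Does the Week 52 RAP name two rival primary measures for mortality and AESIs, and round the wrong one?

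*SAP*

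**What the plan says.** All references are to the Week 52 RAP unless stated.

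- **Section 11** opens with "The primary study summaries will be of overall subject incidence rates of all-cause mortality and AESIs during the on-treatment period".
- **Section 9.5.14** states that "Event incidence rates and subject incidence rates will be calculated for Mortality and Malignancy and other AESIs during the on-treatment and on-study" periods. Its formula is 100 times the subjects with an event, divided by subject-years.
- **Section 11.1.1** calls for the number and percentage of deaths and the difference in percentages with a 95% CI, and adds: "This will be considered as the primary method of assessment of the treatment difference". It expects no difference between arms in exposure or study duration, but says that, to account for one, "supplemental summaries using subject incidence rates will be provided".
- **Section 11.1.2** carries both methods over to the AESIs.
- **Section 11.1** repeats the primary analyses in subgroups, with the limit that "Follow-up adjusted summaries (i.e. subject incidence rate/event incidence rate) will not be included in subgroup tables".
- **Section 8** sets the display rule: "Percentages will be presented to one decimal place. Incidence rates and difference in incidence rates for the primary analyses" get two decimals. The Years 2 to 5 RAP, Section 5.6, adds an exception to the same one-decimal rule: "deaths and malignancies will be presented to 2 decimal places".

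**The concern.** Section 11 uses the exact term that Section 9.5.14 defines on subject-years, so two different quantities appear to hold the lead position. They need not agree: a rate adjusts for time on treatment and a percentage does not. An analyst could in principle see both results and choose which to headline.

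The display rule seems to make this worse. If the percentage difference leads, it would be shown to one decimal while the supplemental rate has two. With about 2,000 subjects per arm one death is 0.05 points, so 9 and 10 deaths would both print as 0.5%. In a study whose whole purpose is estimation with an interval, coarse display of the lead result looks like a real loss. The later RAP gives deaths and malignancies two decimals, which suggests that the sponsor saw the need.

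**Working it through.** **1. Which measure leads?** Apart from the opening sentence of Section 11, the texts agree:

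- Section 11.1.1 names the difference in percentages as primary and the rates as supplemental.
- Section 15.7.1.1 (Appendix 7) gives the main estimand's summary measure as the difference in percentage of deaths.
- Section 11.1 leaves the rates out of the subgroup repeats of the primary analyses. That would be odd if the rates led.
- Section 5.1 sets the precision target on the difference in proportions.

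The RAP also often uses rate or incidence for a plain proportion. Section 5.1 speaks of a first-year mortality rate of 0.68%. Sections 2.3 and 7 state the comparison as a difference in rates. Section 2.2.3 replaces the hazard ratio with a difference in rates. Section 11.2.1 glosses a percentage of subjects as incidence.

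**2. The plan's own figure.** Half-width = 1.96 × √(2p(1−p)/n), with n per arm (Section 5.1, simple asymptotic method).

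- p = 0.68%, n = 2,500: 1.96 × √(2 × 0.0068 × 0.9932 / 2,500) = 0.456 points.
- p = 0.564%, n = 2,000: 1.96 × √(2 × 0.00564 × 0.99436 / 2,000) = 0.464 points.

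Both round to the stated 0.46, so the design precision is that of the percentage difference.

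**3. How far apart could the two measures be?** The documents give no mean follow-up. Assume a deliberately wide gap, 0.95 years on belimumab and 0.85 on placebo, with 2,000 per arm.

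- *Mortality, 12 vs 11 deaths.* Percentages: 0.60 − 0.55 = +0.05 points. Rates: 12/1,900 − 11/1,700 = 0.632 − 0.647 = −0.015 per 100 subject-years. The half-width of the rate difference is 100 × 1.96 × √(12/1,900² + 11/1,700²) = 0.52. The sign flips, but the shift of about 0.065 is roughly one-eighth of the half-width.
- *A commoner AESI, 100 vs 100 subjects* (5%, the serious-infection figure in protocol Table 1-3). Percentages: difference 0. Rates: 100/1,900 − 100/1,700 = 5.26 − 5.88 = −0.62, with half-width 100 × 1.96 × √(100/1,900² + 100/1,700²) = 1.55. The gap is larger here, and this is the situation the supplemental rate is there to show.

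Both results are reported under either reading.

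**4. What does one decimal cost?** Take 2,000 per arm and apply one decimal to differences and limits as well, although Section 8's one-decimal sentence names only percentages.

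| Deaths | Difference (95% CI), two decimals | One decimal |
|---|---|---|
| 11 vs 10 | 0.05 (−0.40, 0.50) | 0.1 (−0.4, 0.5) |
| 21 vs 10 | 0.55 (0.01, 1.09) | 0.6 (0.0, 1.1) |

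Sections 11.1.1 and 11.1.2 require the number of subjects as well as the percentage. From 21/2,000 and 10/2,000 a reader recovers 0.55 ± 1.96 × √((0.0105 × 0.9895 + 0.005 × 0.995)/2,000) = 0.55 ± 0.54 points. No count is hidden and no precision is lost.

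**The case for a change.** The best case for an edit is that loose usage does not excuse this phrase. Section 11 uses the defined term, and Section 11.1 itself lists the subject incidence rate as a follow-up adjusted summary and plots it separately from the percentages. Section 8 also sets percentages and incidence rates in adjacent sentences as if they were different things. On that reading the lead result has one decimal, and in the 21 vs 10 example a lower limit just above zero would print as 0.0.

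The textual point stands: the Section 11 sentence is badly worded, and Section 8 is ambiguous. For the AESIs the percentage is primary only by reference to the mortality method. What does not stand is the harm. The specific section settles the ranking. Sections 2.3 and 8.4 plan no hypothesis test for the safety endpoints, so no decision hangs on a rounded limit. Section 8 applies unless otherwise stated and defers to the mock shells, which are not among the documents and may already fix the decimals.

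Appendix 7 invites two related remarks. It describes the mortality population under primary efficacy analyses, which is a slip, since the population it names (As-Treated) is the right one for safety. It also calls discontinuation irrelevant to the on-treatment estimand, although stopping treatment fixes where that window ends. But the same section states the cut-off of treatment stop plus 28 days, and Section 15.7.1.2 supplies the on-study counterpart. Section 9.1.1 states openly that the on-treatment period leads.

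**Conclusion.** This is a clerical inconsistency with no gain from changing the plan. The primary measure is the difference in percentages, and the rate per 100 subject-years is supplemental. Both are calculated for the on-treatment and on-study periods, and the mortality and AESI tables for both periods are headline results (Section 16.3). Correcting the Section 11 sentence, the decimal rule or the Appendix 7 slip would alter no estimate, interval or conclusion; the most at stake is a second decimal that the reader can compute from the counts. The Years 2 to 5 RAP also records that the Week 52 data were unblinded on 2-JAN-2019 and the analysis completed on 7-FEB-2019, so an edit now could only be a note of clarification. The conclusion rests on the counts being tabulated as Sections 11.1.1 and 11.1.2 require. The follow-up times used above are assumptions and serve only to show scale.
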